#### 2. Group Modifications

Not applicable.

# 3. Method for Assigning Subjects to Groups

After completing the first two TRP depletion test sequences, participants will be randomized to receive either treatment with 17β-estradiol (Vivelle Dot® 0.10 - 0.15 mg/day) or a look-alike placebo patch for a total of 8 weeks. The research pharmacist who is responsible for dispensing the estrogen or placebo patches will also be responsible for the randomization of all subjects together with the statistician on the study. Randomization will be blocked and stratified. We will use a block size of 3 to be able to maintain a 2:1 ratio of estrogen to placebo within each stratum. To stratify randomization based upon time since last menstrual period by tertiles (1st=0-40 mos; 2nd=40-80 mos; 3rd=80-120 mos), we will prepare separate randomization tables for each stratum. The research pharmacist, PI, and research project manager will know to which group the subject has been randomized. The research pharmacist, PI or research project manager can be reached at any time should it become necessary to unblind a study participant immediately. The subject and all other study-related personnel (clinicians, raters, fMRI technicians, etc.) will be blind to subject assignment.

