#### 5. Early Withdrawal of Subjects

Early withdrawal of subjects may occur for the following reasons:

- 1. If the subject fails to return for visits.
- 2. Failure to locate the subject.
- 3. The subject withdraws their consent for participation.
- 4. The PI determines that the subject is no longer eligible for participation in the study.

A subject can withdraw their consent for participation in this study by contacting the study PI and or the research staff personnel who is following them in the study via telephone and informing them of their decision. In this case it would be preferable if the subject is willing to come in to the office for a debriefing regarding whether or not to continue estrogen treatment under the care of their personnel physician. If this is not possible, then the PI will speak with the subject by telephone to conduct this debriefing and find out whether or not the subject plans to stay on estrogen treatment. The subject's decision to withdraw and their disposition upon withdrawing from the study will be recorded in their research chart.

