# STUDY PROCEDURES

# 1. Detailed Description

This study involves TRP depletion, evaluation of cognition, and the use of fMRI during cognitive and affective task performance both before and after estrogen or placebo treatment (PT). There will be four successful\* TRP depletion test sequences: two test sequences one week apart prior to ET or PT, and two sequences one week apart following approximately 6-weeks of double-blind ET or PT. Each TRP depletion test day will involve ingestion of 70 capsules. During one of each pair of tests, the 70 capsules will contain 31.5 g of lactose (sham depletion; for participants who are not lactose intolerant) or 31.5 g of microcellulose (sham depletion; for participants who have mild to moderate lactose intolerance), while during the other test they will contain a total of 31.5 g of amino acids, but no tryptophan (see below; Neumeister et al., 2004; Neumeister et al., 2005). The order of the tests (sham vs. active depletion) will be randomly assigned in double blind fashion by the research pharmacist. Imaging procedures will take place on each of the test days. Subjects will be required to remain at the Center for Human Phenomic Science (CHPS) for the entire Test Day except during the fMRI scan.\*\*

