For the peri- and post-menopausal women participating in our previous tryptophan depletion/estrogen study (Amin et al., 2006b), mean baseline estradiol level was 31.72 pg/ml. With the 0.10 - 0.15 mg/d estradiol dose, mean estradiol levels were 96.33 pg/ml. Thus, our goal is to achieve a similar increase in estradiol in subjects participating in the present study. These doses are higher than the lowest available and may be higher than the lowest effective dose, which is the standard in clinical practice. However, in this experimental context, it is necessary to have a significant increase in plasma estradiol level in order to evaluate estrogen's effects. In addition, the standard dose in clinical practice is recommended for long-term ET. The proposed short-term ET regimen (chosen to more closely mimic the cyclic regimens currently recommended) is not likely to be associated with as significant risks as long-term ET. In our previous study, although women with greater time since LMP were found to have lower pre-treatment estradiol levels, the relationship between time since LMP and estradiol was less negative following ET, suggesting increased similarity among participants. Nevertheless, we will control for both age and plasma estradiol level when examining effects of time since LMP.

Following completion of approximately 6 weeks of ET or PT, the subjects will participate in the last two TRP depletion test sequences (one sham and one active depletion). Upon completion of the 4th test day (or use of estrogen for at least 2 weeks in those who drop out), all subjects will be debriefed regarding their active vs placebo patch status and subjects randomized to ET will take Prometrium (micronized progesterone USP encapsulated with peanut oil) 200 mg daily or medroxy progesterone 5 mg/d (for women with peanut allergies) for 12 days. Prometrium and medroxy progesterone are USFDA approved for antagonism of estrogen effects on the endometrium in women taking hormone treatment (HT). According to a review of studies of oral progesterone in menopausal women, use of progesterone,

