the progestational steroid produced by the human corpus luteum, minimizes side effects seen with synthetic progestins (McAuley et al., 1996). Long-term protection of the endometrium by Prometrium given as 200 mg/day for 12 days/month or medroxy progesterone given as 5 mg/d has been established (Gibbons and Thorneycroft, 1999). Oral micronized progesterone at a dose of 200 mg/ day is well-tolerated, with the only specific side effect being mild and transient drowsiness. Those women who would like to continue hormone therapy will be prescribed 3 additional months of estrogen (as well as an additional Prometrium treatment for women who have an intact uterus) and then referred to their gynecologist for continued treatment. The participant or her insurance company will be responsible for covering the cost of the additional treatment. Those women who wish to discontinue their HT will do so after cycling themselves with Prometrium or medroxy progesterone for 12 days. After the 12 days of Prometrium or medroxy progesterone with the Vivelle patch, women will discontinue both hormones.

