Use of venipuncture for blood sampling: Inserting a needle into a vein is safe when done by professionals under clean conditions. Sometimes a bruise will occur at the puncture site and on rare occasions fainting, a blood clot, or an infection may form in the vein. If this occurs, appropriate treatment will be instituted immediately.

Behavioral Assessments: Subjects may feel upset when answering questions on the TLEQ and ACE. Should a subject report or appear distressed about the feelings that arise from answering these questions, then arrangements will be made for the subject to see the study doctor for an assessment immediately. All subjects reporting significant distress, homocidality, or suicidality, will be evaluated by a trained psychiatrist (P.I. and co-P.I.) and a decision about emergency treatment versus referral will be made. If participants opt to complete the ACE over the phone and experience distress the same arrangements will be made for participants to speak with a study doctor about their distress.

Nonspecific risks: As a result of their participation in these studies, subjects will have more blood drawn than would be the case in usual clinical practice. The maximal amount of blood subjects will have drawn will be less than one blood donation (85 cc), spread out over a period of 1-8 weeks.

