#### 6. Data and Safety Monitoring

This protocol presents moderate risks to the subjects, and these risks are defined as due to the study procedures and treatments although there are adequate protections to minimize these risks. In order to minimize the risks of participating in this study, we will carefully monitor all subjects and all serious unanticipated and anticipated adverse events. Any unanticipated adverse events will be reported to the IRB within 10 days of their occurrence. In the case of death, it will be reported to the IRB within 3 days. The principal investigator ([name]) is responsible for making these reports to the IRB. [name] or another study doctor will review all adverse events as they occur. [name] will evaluate frequency and severity of the adverse events and determine if modification to the protocol or consent forms is required. In addition, [name] will code the severity of adverse events and determine attribution of the event. These events will be summarized in our annual request for reapproval application to the IRB.

In addition, all subjects who sign the consent form are required by the protocol to submit mammogram, Pap smear, and breast exam results from their doctor (results must be within the past year) prior to beginning the study. This insures that all subjects have been examined by their gynecologists prior to enrolling in the study. We also send a courtesy letter to the gynecologist (after obtaining a signed release of information form) informing him or her of their patient's intentions to participate in this study.

Vivelle-Dot® is manufactured by Noven Pharmaceuticals, Inc., and is being purchased from Novartis using study funds through Investigational Drug Services as needed. . These companies ask that in the event of an adverse event that we submit an adverse event report immediately.

The research pharmacist, PI, and research project manager will know to which group the subject has been randomized. The research pharmacist, PI or research project manager can be reached at any time should it become necessary to unblind a study participant immediately. The subject and all other study-related personnel (clinicians, raters, fMRI technicians, etc.) will be blind to subject assignment.

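### The PI and project manager know each woman's estrogen/placebo group in a phase called double-blind, which exposes discretionary withdrawals and adverse-event coding, though not the rated or scanned outcomes

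*Combined protocol and SAP*

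**What the plan says.** Methods section 3 (Method for Assigning Subjects to Groups) says "The research pharmacist, PI, and research project manager will know to which group the subject has been randomized". The same sentence appears in the section on randomization to estrogen treatment (ET) or placebo treatment (PT), and again in Data and Safety Monitoring. Each time, the subject and all other personnel, with clinicians, raters and fMRI technicians as examples, are said to be blind. The pharmacist, PI and project manager can all be reached at any hour to unblind a woman. The statistician shares responsibility for randomization but is not listed among those who know the arm.

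The Detailed Description of study procedures calls for "two sequences one week apart following approximately 6-weeks of double-blind ET or PT".

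The PI's duties during treatment are spread over several sections:
- Early Withdrawal of Subjects lists as one reason: "The PI determines that the subject is no longer eligible for participation in the study".
- The Investigator's Risk/Benefit Assessment puts the PI on call for problems, in a paragraph about test sessions.
- Data and Safety Monitoring makes the PI responsible for adverse-event reports to the IRB, and then says that a person whose name is removed "will code the severity of adverse events and determine attribution of the event".

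Some tasks do use the arm. A woman who withdraws is offered "a debriefing regarding whether or not to continue estrogen treatment under the care of their personnel physician". After the fourth test day (or at dropout after at least 2 weeks of estrogen) "all subjects will be debriefed regarding their active vs placebo patch status", women on ET receive progesterone, and "Those women who would like to continue hormone therapy will be prescribed 3 additional months of estrogen".

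**The concern.** Attribution is a judgement about whether treatment caused an event, and deciding that a woman is no longer eligible can also involve judgement. Knowledge of the arm can colour both. The plan describes clinicians as blind, yet the PI carries clinical duties and is not blind. The only reason given for the PI and project manager to hold the arm is emergency unblinding, which the pharmacist already covers.

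Two things are at stake: the adverse-event summary that goes to the IRB, and who is retained through test days 3 and 4. The arms are small, so retention matters: one discretionary withdrawal is 1/14 = 7.1% of the placebo arm or 1/28 = 3.6% of the ET arm.

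**Working it through.** The plan gives no figure on this point to reproduce, so the check is mainly a comparison of sections.

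**When is the arm needed?**

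| Task | When | Arm needed during treatment? |
|---|---|---|
| Emergency unblinding | Any time | Only for that woman; pharmacist already reachable |
| Debriefing of a woman who withdraws | After she withdraws | No |
| Patch-status debriefing, progesterone, further prescribing | After test day 4, or at dropout | No |
| Eligibility withdrawal by the PI | During the study | No |
| Evaluating problems at test sessions | Test days | No, emergencies apart |
| Coding severity and attribution | As events occur | No |

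No stated task, emergencies apart, needs the arm before withdrawal or test day 4.

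**How many women, and for how long?** Specific Aim 2 gives 28 ET + 14 placebo = 42. Randomization follows test day 2. Test day 3 comes after about 6 weeks of patch and test day 4 one week later, so the exposed period is about 6 + 1 = 7 weeks per woman. This reads the quoted sentence as applying from randomization, since no later date is given.

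**Who codes events?** The sentence gives only a removed name. The same paragraph introduces the PI as responsible for the reports and then continues with the removed name, so the PI is the natural reading, but not a stated fact.

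**Secondary: how predictable is the list to someone who knows it so far?** Blocks are fixed at 3 (two ET, one placebo) within each stratum of time since last menstrual period. The three orders are equally likely:
- PEE: after P, positions 2 and 3 are certain (2 certain).
- EPE and EEP: only position 3 is certain (1 certain each).

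The mean per complete block is (2 + 1 + 1)/3 = 4/3 of 3 assignments, or 4/9 = 44.4%. A leftover pair adds 1 certain assignment with probability 1/3.
- 14 women per stratum (4 blocks plus 2): 3 × (4 × 4/3 + 1/3) = 17.0 of 42 = 40.5%.
- All blocks complete (for example 15/15/12): 14 × 4/3 = 18.67 of 42 = 44.4%.
- Other splits over three strata fall between these.

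Best-guess accuracy at 14 per stratum: a complete block gives 2/3 + 2/3 + 1 = 7/3 expected correct, and a leftover pair 4/3. That is (4 × 7/3 + 4/3)/14 = 76%, against 67% from always guessing ET.

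**The case against.** The arrangement is disclosed in identical words three times. Subjects and assessors are blind, and many trials would call that double-blind. This stands, and it is why the matter is a limited gap in blinding and not a concealed one. Disclosure does not remove the exposure, however.

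The evidence on the PI's discretion is thinner than it first looks. Subject Follow-up gives mostly objective examples of lost eligibility, such as imprisonment or commitment to hospital. Data and Safety Monitoring allows another study doctor, who would be blind, to review events. Two of the four test sessions precede randomization. The Risks section names the PI as evaluating distressed women, but that passage concerns distress from the trauma and childhood-adversity questionnaires and names the co-PI as well; only the childhood-adversity questionnaire is repeated after randomization, at test day 3. I place no weight on it. All of these limits stand. They narrow the exposure, but they do not assign coding or eligibility decisions to a blind person.

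The Statistical Analysis section plans no adverse-event comparison between arms, so no planned test is directly affected. That also stands.

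A reader might infer more than the documents support:
- That recall or fMRI results are biased. Raters and technicians are blind, and no section has the PI give the test-day ratings.
- That the sham/active capsule blind is broken. It is a separate double-blind assignment.
- That the PI is known to code adverse events. This is inference only.
- That predictable blocks let staff steer enrolment. Randomization comes after enrolment and both baseline test days. Only a withdrawal in the gap before randomization could be affected, and nothing suggests that this happens.

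**Conclusion.** The point holds in a limited form. The PI and project manager know the arm with no stated delay, in a phase labelled double-blind, and the PI has duties that knowledge of the arm can influence. The exposure is confined to discretionary withdrawals and the adverse-event record, for 42 planned women over about 7 weeks each. It rests on two readings: that knowledge begins at randomization, and, for event coding, that the removed name is the PI. If the second is wrong, the withdrawal and problem-evaluation roles remain. No bias has been shown; this is an avoidable risk with a cheap remedy.

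The block arithmetic (about 40% to 44% of assignments certain) applies only to someone who knows the block size and every earlier assignment in order within the stratum. It is a further reason to withhold the arm from the PI and project manager, and not a separate fault.

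**What to change.** 1. In the three places where the sentence appears, limit knowledge of the arm during treatment to the research pharmacist, with sealed emergency codes as round-the-clock backup. State the statistician's status: if a statistician must hold the list, a different person, blind to arm, should analyse the data until the data are locked.
2. In Early Withdrawal of Subjects and the ET/PT randomization section, have the pharmacist release a woman's arm to the debriefing doctor only after test day 4, or after her withdrawal and its reason are recorded, emergencies excepted. The treatment steps that follow stay as written.
3. In Data and Safety Monitoring, require that severity and attribution of events up to that point be coded before release, or by a blind study doctor. Acknowledge that later events are coded unblinded.

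No change of block size is needed. Randomly mixed blocks of 3 and 6 would lower best-guess accuracy only from 76% to 74% for someone with full knowledge, and withholding the arm removes that knowledge.

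The cost is protocol wording, sealed codes and a release step. Two of the three unblinding contacts lose that role, so emergency unblinding would go through the pharmacist or the sealed code. Events after release, including those in the 12-day progesterone phase, remain coded unblinded.

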# 4. Administration of Surveys and/or Process

Assessments to be administered during the intake interviews:

- Demographic information including age, education, income, health insurance status, marital status, and race;
- Full gynecologic history including age at menarche, menstrual cycle length/regularity and menstrual cycle-related changes in mood and behavior, obstetrical history, mood related to pregnancies, and onset of menopausal symptoms and menstrual irregularity;
- Information about family history of psychiatric disorders, alcoholism, and nicotine dependence in parents and siblings (obtained from subject report);
- Structured Clinical Interview for Diagnosis (SCID; First et al., 1997);
- Mini-Mental State Examination (MMSE);
- The Profile of Mood States (POMS; McNair et al., 1992);
- Utian Quality of Life Questionnaire (Utian QoL; Utian et al., 2002);
- Pittsburgh Sleep Quality Index (PSQI; Buysse et al., 1989);

- Clinician Administered PTSD Scale (CAPS; Blake et al., 1995);
- Social Support Scale (SSS; Zimet et al., 1998);
- Hamilton Depression Scale (HAM-D; Hamilton, 1960);
- Traumatic Life Events Questionnaire (TLEQ; Kubany et al, 2000);
- Adverse Childhood Experiences (ACE; Felitti et al., 1998)—to be assessed over the phone OR during the in-office admission-screening process;
- Brief COPE (Carver, 1997);
- Perceived Stress Scale (PSS; Cohen at al., 1983).
- Beck Depression Inventory (BDI)
- The Speilberger State-Trait Anxiety Scale (STAI; Spielberger et al., 1983)
- Visual Analogue Scale (VAS)

Assessments to be administered on test days:

- The Profile of Mood States (POMS; McNair et al., 1992);
- Visual Analogue Scale (VAS);
- Daily Hot Flash (HF Diary).
- Beck Depression Inventory (BDI)
- Perceived Stress Scale (PSS; Cohen at al., 1983).
- The Speilberger State-Trait Anxiety Scale (STAI; Spielberger et al., 1983)
- Hamilton Depression Scale (HAM-D; Hamilton, 1960);
- Pittsburgh Sleep Quality Index (PSQI; Buysse et al., 1989)—test days 2 and 4 only;

#### 5. Data Management

Research data will be collected and recorded on case report forms specifically designed for this study. Data will be entered into a study database on a non-portable computer which is password protected. All of the information obtained from subjects is quoted by number and kept in locked confidential files. This information is not available to anyone except the investigators and study staff, and is not identified by the subject's name. The investigators and anyone else involved with this project are not allowed to reveal any identifying characteristics about the patients who participate in this study without their written consent. In the case of published reports from this study, care will be taken so that no individual subject will be identifiable.

All data will be stored in a locked file cabinet in a secure area of the clinic. Only those investigators directly involved with the project have access to this information. The researchers and study personnel involved with this project will abide by all regulations to keep subject's participation in this study confidential. However, a limit to confidentially exists in the possibility that a subject may discuss with friends and family their participation in this study. In addition, we as the investigators and study personnel are legally required to report abuse of children, elders or that the subject is a danger to themselves or others.

When the research is complete, the data will be stored in a locked file cabinet for up to 7 years. After 7 years, the study data will be archived with a professional medical records archive company.

# 6. Management of Information for Multi-Site Research where a Penn Investigator is the Lead Investigator of a Multi-Site Study, or Penn is the Lead Site or Coordinating Center in a Multi-Site Study.

Not applicable.

# 7. Subject Follow-up

Multiple subject visits are a required for this study. Efforts will be made to engage the subjects in the importance of the project, their participation, and what they are gaining from participating (i.e., psychiatric work up, medical testing, and free short-term estrogen treatment). If a subject is lost to the study before all the data is collected, we will make every attempt to contact that person via telephone and mail. However, these attempts sometimes fail and subjects are permanently lost to follow up.

If the subject is imprisoned, committed to a mental hospital, hospitalized for long term care, admitted to a drug/alcohol residential program, or a residential living facility or alike during the course of their participation in the study, then the subject would no longer be eligible to participate in the study because these circumstances would indicate that the subject no longer met study criteria (i.e., due to onset of psychiatric or drug/alcohol problem or incarceration which would prevent them from participating).

